Pain is an undesirable consequence of surgery especially cardiac surgery as pain during and following cardiac surgery has been shown to be a risk factor for increased morbidity. Systemic opioids have been the main stay for the management of perioperative pain in cardiac surgery. Lower doses of opioids has been related to early extubation and minimizing opioid-related side effects, such as prolonged ventilation, tolerance, nausea, vomiting, gut dysfunction, and immunosuppression.

On the other hand we find cases of morbidity and mortality not related to the surgical procedure. ERAS protocol discuss the optimum condition that can we use to avoid the morbidity and mortality complications.

We aim to know how well ERAS protocol is known and applied

Aim of the work

Our aim is to know how well cardiac anesthesiologists, cardiac intensivists and cardiothoracic surgeons know and apply ERAS protocol in mitral valve surgery.

Objectives:

We will use the questionnaire about ERAS guidelines to assess the knowledge of doctor about the guidelines.

Hypothesis:

Our hypothesis is that ERAS guidelines are not well known among doctors.

Ethical Considerations

The study will be conducted after taking approval of the research and ethical committees.

Informed consent will be obtained from study participants or their legally authorized representative.

Methodology

I. Study design

Cross section study to assess of knowledge about Enhance Recovery After Surgery (ERAS) guidelines between cardiac anesthesiologists, cardiac intensivists and cardiothoracic surgeons.

II. Study setting and location

- Anesthesia department, Cairo university hospitals, kasr al-ainy.
- Cardiothoracic thoracic surgery department, Cairo university hospitals, kasr al-ainy.
- Anesthesia department, National Heart Institute.
- Cardiothoracic surgery department, National Heart Institute.

III. Study population

- Cardiac anesthesiologists
- Cardiac intensivists
- Cardiothoracic surgeons

IV. Eligibility Criteria

1. Inclusion criteria

- Cardiac anesthesiologists.
- Cardiac intensivists.
- **Cardiothoracic surgeons.**
- All staff members from resident to consultant are included inside this study

V. Study Procedures

1. Randomization (in RCT only)

A questionnaire **will be sent online** to a random sample of anesthesiologists and intensive care physicians.

The random sample will be taken by use of random list.

2. Study Protocol:

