The questionnaire consists of number of questions that the doctor has to answer in a set format. It will be a closed-ended questions:-

- Dichotomous
- Nominal-polytomous
- Ordinal-polytomous

Grading system will be described as:-

- Grade A (knows well (: more than 60 % correct answer
- Grade B (fair): 35 :60 % correct answer
- Grade C (knows nothing) :- less than 35 % correct answer

2. Measurement tools

1. Questions about ERAS society
2. Questions about premedications
3. Questions about opioids
4. Questions about ERAS guidelines :-
 - Preoperative Hb A_{1c} measurement
 - Preoperative measurement of Albumin
 - Preoperative correction of nutritional deficiency
 - Consumption of clear liquid before GA
 - Preoperative carbohydrates loading
 - Prehabilitation

VI. Study outcomes

1. Primary outcome

Assesment of the knowledge of doctors to ERAS guidelines in cardiac surgery by using the grading system.

2. Secondary outcome(s)

Statistical Analysis

I. Sample size

The sample size had determined using epi-infoVersion 7 based on the following prerequisites:

- Confidence level = 95%
- Expected frequency of knowledge about Enhance Recovery After Surgery (ERAS) guidelines between cardiac anesthesiologists, cardiac intensivists and cardiothoracic surgeons = 50%.

- Confidence limit =5%

- Population size = 1000 (cardiac anesthesiologists, cardiac intensivists and cardiothoracic surgeons in Cairo University hospitals (Koir Al Ainy) and National Heart Institute).

This gave a minimum sample size two hundred and seventy eight physicians had selected to be included in the study.

II. Statistical analysis

The collected data will be revised, coded and analyzed using SPSS version 21 software for tabulation and analysis.

The following statistical measures will be calculated:

A. Descriptive statistics:

1- Count and percentage.

2- For quantitative variables, arithmetic mean and standard deviation will be calculated.

B. Analytical statistics:

The data will be analyzed and when $p<0.05$ will be considered statistically significant.

References

[1] Scott MJ, Baldini G, Fearon KC, Feldheiser A, Feldman LS, Gan TJ, Ljungqvist O, Lobo DN, Rockall TA, Schricker T, Carli F. Enhanced Recovery After Surgery (ERAS) for gastrointestinal

surgery, part 1: pathophysiological considerations. Acta Anaesthesiol Scand. 2015 Nov;59(10):1212-31. doi: 10.1111/aas.12601. Epub 2015 Sep 8. PMID: 26346577; PMCID: PMC5049676.

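### The primary grade uses raw percent correct on closed-ended items with no stated allowance for guessing; if yes/no items are scored, an uninformed guesser can be graded 'fair' or better

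*Combined protocol and SAP*

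**What the plan says.** The Study Protocol subsection of Study Procedures describes the instrument in two sentences: "The questionnaire consists of number of questions that the doctor has to answer in a set format" and "It will be a closed-ended questions". It lists three formats: dichotomous, nominal-polytomous and ordinal-polytomous. Each doctor is then placed in one of three grades:

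- "Grade A (knows well (: more than 60 % correct answer"
- "Grade B (fair): 35 :60 % correct answer"
- "Grade C (knows nothing) :- less than 35 % correct answer"

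The primary outcome is "Assesment of the knowledge of doctors to ERAS guidelines in cardiac surgery by using the grading system". The secondary outcome heading has nothing under it, so the grade is the only stated outcome.

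The plan mentions no correction for guessing, no negative marking, no 'don't know' answer, no rule for blanks and no reason for the cut-offs. It does not give the number of items, the options per item, the share of yes/no items, or which items are scored. The questionnaire is not reproduced, so a 'don't know' answer may exist in it.

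**The concern.** The bottom grade is meant to pick out doctors who know nothing. On a yes/no item such a doctor is right half the time by guessing, and 50% falls in the middle grade. For that format the label and the scoring rule disagree.

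What is at stake is the grade distribution itself. The aim is to learn how well these doctors know the guidelines, so the A/B/C split is the result. If guessing moves uninformed doctors from C to B, the share graded C is too low and the share graded B too high. A larger sample does not remove this, because it is bias and not sampling error.

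**Working it through.** **The plan's own figure.** Inputs from the Sample size section: population N = 1000, expected frequency p = 0.50, margin d = 0.05 ("Confidence limit =5", in percent), 95% confidence (z = 1.96).

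n = N·p(1−p) / [(d²/z²)(N−1) + p(1−p)] = 250 / [(0.0025/3.8416) × 999 + 0.25] = 250 / 0.9001 = 277.7, rounded up to 278. This reproduces the stated sample size. The guessing problem does not touch it.

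**Inputs for the guessing check.** From the plan: Grade A if the score is above 60%, Grade C if below 35%, otherwise B. Assumed, because the plan is silent: all items in the mix are scored, one correct option per item, no 'don't know' answer, no blanks, and a guesser picks uniformly at random. The chance of a correct answer is then 1/2 for yes/no, 1/4 for four options and 1/5 for five.

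**Method.** The number correct is binomial when all items have the same format, and the sum of two independent binomials when formats are mixed. Example with 10 yes/no items: Grade C needs 3 or fewer correct, with probability (1 + 10 + 45 + 120)/1024 = 0.172. So 82.8% are graded B or A. Grade A needs 7 or more, which by symmetry also has probability 17.2%.

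**Share of pure guessers graded B or A**

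| Item mix | 10 items | 20 items | 30 items |
|---|---|---|---|
| All yes/no | 83% | 94% | 95% |
| Half yes/no, half four-option | 56% | 68% | 61% |
| 30% yes/no, rest four-option | 42% | 49% | 37% |
| All four-option | 22% | 21% | 11% |
| All five-option | 12% | 9% | 3% |

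The figures do not move smoothly with length because scores are whole numbers.

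**Break-even.** With yes/no share s and the rest four-option, the expected chance score is 0.5s + 0.25(1−s). Setting it equal to 0.35 gives s = 0.10/0.25 = 0.40. Above 40% yes/no items, the average guesser scores over the Grade C ceiling.

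**Grade A from pure guessing.** At 10/20/30 items: 3/1/0.3% (half yes/no, half four-option) and 17/13/10% (all yes/no). At 6 items the half-and-half mix gives 14%.

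**Partly informed doctors.** One who knows 8 of 20 items (40%, Grade B) and guesses 12 is graded A with probability 49% (half and half), 16% (all four-option) or 81% (all yes/no).

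**Against the planned margin.** If 10% of doctors guessed throughout (an assumption), the shift out of Grade C is 0.10 times the table entry. At 10/20/30 items that is 5.6/6.8/6.1 points (half and half), 4.2/4.9/3.7 (30% yes/no) and 2.2/2.1/1.1 (all four-option), against ±5 points. The plan does not say which grade counts as knowledge for that margin.

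**The case against.** The strongest reply is that the instrument is not visible. Dichotomous is listed as a format of the questionnaire, not of the graded items. The aim covers applying the guidelines as well as knowing them, so some yes/no items may ask about practice or awareness and have no correct answer. The phrase about answering in a set format may only describe closed-ended items and need not mean forced answers. All of this stands, and it is why the point is conditional.

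Second, pure guessing is a harsh model for cardiac specialists. Doctors with misconceptions do worse than chance: if the correct answer is picked 40% of the time on yes/no and 20% on four-option items, the half-and-half figures at 10/20/30 items fall to 35/39/27%. The partly informed example also sits close to the cut-off (expected score 8 + 4.5 = 12.5, where Grade A needs more than 12), so it is not a typical shift. Both stand as limits on size, not on the mechanism.

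Third, the bias runs against the hypothesis, "Our hypothesis is that ERAS guidelines are not well known among doctors". This also stands. A reader might infer that a finding of poor knowledge would be unsafe; the reverse holds, because guessing makes such a finding harder to reach.

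A reader might also infer that a mostly 'fair' result would be indistinguishable from guessing. That goes too far. Guessing throughout on 20 half-and-half items gives A 1%, B 67%, C 32%, so a mostly 'fair' sample with clearly fewer than 32% in Grade C would not fit that pattern. What holds is that such a result is hard to interpret unless the chance score is reported with it.

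**Conclusion.** The point holds in conditional form. The plan states no allowance for guessing, and chance on a yes/no item lies above the ceiling of the lowest grade. If yes/no items are scored and there is no 'don't know' answer, uninformed doctors who guess can be graded B or A. The B versus C split is most exposed. Movement of pure guessers into Grade A is small for mixed tests of 10 to 30 items, but not for very short or all yes/no tests.

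The documents do not support the stronger reading that most uninformed doctors would pass as 'fair'. Over the mixes in the table the share at 10 to 30 items runs from 3% to 95%, and nothing in the plan says where this questionnaire lies. The mechanism is certain; the size is not. It should be fixed because it affects the only stated outcome and is cheap to reduce before data collection.

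**What to change.** Before launch:

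1. Add 'I don't know' to each scored item that lacks it, count it as not correct, say so to respondents, and ask them to choose it rather than guess.
2. Keep the 35% and 60% cut-offs on raw percent for the primary grade.
3. Report the expected chance score of the scored items (mean of 1/options, not counting 'I don't know') beside the A/B/C distribution. As a sensitivity analysis only, also report the grades on a chance-corrected percent: (raw − g)/(1 − g), with raw and the chance score g taken over items answered other than 'I don't know', times the share of items so answered (0 if none).

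The cost is one answer option per scored item, one instruction line and one scoring paragraph. The sample size of 278 is unchanged. The answer option cannot be added once responses are in.

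Downsides: somewhat fewer doctors will be graded A or B, and a cautious doctor will score lower than an equally informed one who guesses. The gain depends on use. With the half-and-half mix at 10/20/30 items, an uninformed doctor who chooses 'I don't know' half the time is graded B or A in 10/6/1.5% of cases, but in 30/32/19% if it is chosen a quarter of the time. Guessers who ignore it are still misgraded on the raw grade; the corrected percent grades them B or A in 12/3/1% of cases. The corrected percent can also undergrade partly informed doctors: on 20 yes/no items, one who knows 8 and guesses the rest is graded C 39% of the time. That is why it should not replace the primary grade.

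### The plan names no questionnaire item for specialty, cardiac practice, rank or institution, and its sampling sentence does not match its eligibility criteria

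*Combined protocol and SAP*

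**What the plan says.** All references are to the combined protocol and SAP.

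- **Aim:** "Our aim is to know how well cardiac anesthesiologists, cardiac intensivists and cardiothoracic surgeons know and apply ERAS protocol in mitral valve surgery".
- **Study design:** "Cross section study to assess of knowledge about Enhance Recovery After Surgery (ERAS) guidelines between cardiac anesthesiologists, cardiac intensivists and cardiothoracic surgeons".
- **Eligibility Criteria:** the three cardiac specialties, with the addition "All staff members from resident to consultant are included inside this study".
- **Study setting and location:** two anesthesia departments and two cardiothoracic surgery departments, one of each at Cairo University hospitals and at the National Heart Institute. No intensive care department is listed.
- **Randomization:** the online form goes "to a random sample of anesthesiologists and intensive care physicians", drawn by means of a random list. The list's fields are not described, and no link from list to response is stated.
- **Measurement tools:** four blocks, covering the ERAS society, "Questions about premedications", opioids, and the ERAS guidelines with six clinical sub-topics. The individual questions are not reproduced.
- **Study outcomes:** the primary outcome is doctors' knowledge on the A/B/C grading system. No secondary outcome is given.
- **Sample size:** one proportion, in a population of 1000 made up of the three cardiac specialties at the two institutions.
- **Analytical statistics:** "The data will be analyzed and when $p<0.05$ will be considered statistically significant". No test or grouping variable is named.

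**The concern.** The conclusion is to be about three cardiac specialties at two institutions, across all ranks. The questionnaire is the only data source described, and every block listed for it is a knowledge topic. Nothing in the plan therefore establishes who answered.

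That would matter less if being sampled guaranteed eligibility. The sampling sentence drops the word *cardiac* and omits surgeons. Followed literally, it can admit anesthesiologists and intensive care physicians who do no cardiac work, and it can leave out one of the three specialties altogether. No later step in the plan catches either problem.

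The hypothesis is that the guidelines are poorly known. If non-cardiac respondents know cardiac ERAS less well, which is plausible but not documented, including them moves the result toward that hypothesis. If responses to the online form are not linked to identities, the missing fields cannot be recovered after data collection.

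**Working it through.** **1. The plan's own figure.** Inputs from the Sample size section: population N = 1000, expected frequency p = 0.50, confidence limit d = 0.05, confidence level 95% (z = 1.96). The finite-population formula for one proportion is

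n = N·p(1−p) / [(d²/z²)(N−1) + p(1−p)]

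= 250 / [(0.0025/3.8416)(999) + 0.25] = 250 / 0.9001 = 277.74, rounded up to 278.

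The stated 278 reproduces. It is a precision calculation for one pooled proportion, so recording respondent characteristics does not change it.

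**2. Whom the plan wants against whom it samples.**

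| Characteristic | Eligibility and population of 1000 | Sampling sentence | Questionnaire item named |
|---|---|---|---|
| Anesthesia | cardiac only | not limited to cardiac | none |
| Intensive care | cardiac only | not limited to cardiac | none |
| Cardiothoracic surgery | included | not mentioned | none |
| Rank | resident to consultant | not mentioned | none |
| Institution | two | not mentioned | none |

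The sampling sentence differs from the target in both directions: it is too wide on cardiac practice and too narrow on surgeons. Department would not recover specialty even if it were known, because the settings are anesthesia and surgery departments only. Department alone cannot separate cardiac intensivists from anesthesiologists.

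**3. Size of any bias.** If a share c of respondents is non-cardiac and their proportion in a given grade differs from that of cardiac staff by g points, the pooled proportion shifts by c × g points. The documents give neither c nor g, so no value can be computed.

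**4. What results by specialty could show.** Assume three equal groups of 278/3, about 93 (group sizes are not in the documents). At p = 0.50 the 95% half-width is

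1.96 × √(0.25/93) = 0.102, or ±10.2 points.

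With a finite-population correction, assuming 1000/3 (about 333) physicians per specialty, it is about ±8.6 points. The pooled estimate with its correction is

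1.96 × √[(0.25/278) × (722/999)] = 0.050, or ±5.0 points.

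**The case against.** **The study is pooled.** A reader might infer from the word *between* that the design promises a comparison of specialties which the form cannot deliver. The documents do not support that. The Sample size section applies the same phrase, "guidelines between cardiac anesthesiologists, cardiac intensivists and cardiothoracic surgeons", to a single expected frequency of 50%, which cannot be a contrast, so the word most likely means *among*. The hypothesis and the primary outcome speak of doctors as one group, no secondary outcome is given, and the significance line names no groups. One pooled grade distribution is what the plan sets out to produce. This part of the objection stands.

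**The items may exist.** The questionnaire is not reproduced and the list gives topics only. A section on respondent details, or fields on the random list, could hold this information. It would therefore go too far to say that the study collects none of it; the plan names none of it. The action is the same either way: write the items in if they exist, and add them if they do not.

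**Eligibility is otherwise consistent.** The cardiac restriction appears in the aim, design, study population, inclusion criteria and population of 1000. The sampling sentence may be loose drafting under a template heading, and the setting "Anesthesia department, National Heart Institute" is by its name in a cardiac center, so the risk may be smaller there. This is fair as to likelihood. Even so, that sentence is the plan's only statement of who is sent the form, and nothing later corrects it.

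**No bias threshold can be given.** A reader might also infer a contamination level at which the bias exceeds the planned 5 points. That level depends wholly on an assumed knowledge gap: 5/30 = 17% for a 30-point gap, but 5/10 = 50% for a 10-point gap. Neither gap is in the documents.

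**Conclusion.** The point holds as an omission joined to an inconsistency. The plan names no item for specialty, cardiac practice, rank or institution, and its sampling sentence conflicts with its eligibility criteria. As written, ineligible respondents cannot be identified or removed, and the pooled result cannot be shown to represent the 1000 physicians it is meant to describe.

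The omission itself rests on no assumed figure. The size of any bias is unknown, and its direction (toward the hypothesis) depends on the undocumented premise that non-cardiac respondents know less. The point does not invalidate the pooled primary outcome or the 278, and it does not show that a promised comparison has failed. It should be corrected before the form is sent, because the information may not be recoverable later.

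**What to change.** 1. Add an opening block to Measurement tools, answered before any knowledge question, with four closed items: specialty (cardiac anesthesia, cardiac intensive care, cardiothoracic surgery, none of these); currently works with cardiac surgical patients (yes/no); broad rank category; institution.
2. End the form for anyone who answers none of these or no, and replace them from the same random list.
3. Reword the sampling sentence to match the eligibility criteria: cardiac practice required, surgeons included. The screen-out alone cannot bring in surgeons who were never sent the form.
4. Keep the pooled grade distribution as the primary outcome. Report grades by specialty, rank and institution as descriptive estimates with 95% intervals only, and state that 278 was sized for one pooled ±5-point estimate. Specialty should not become a tested comparison: with 93 per group (assumed), power at two-sided 0.05 is only about 28% for 50% against 60%.

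The cost is four short extra questions, some replacement invitations, and slightly less anonymity, which broad rank categories limit. The sample size does not change.

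### Does the sample size of 278 fall short because it makes no allowance for doctors who do not answer the online questionnaire?

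*Combined protocol and SAP*

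**What the plan says.** The combined protocol and SAP sizes the survey in Statistical Analysis, I. Sample size. The inputs are "Confidence level = 95" per cent, "Expected frequency of knowledge about Enhance Recovery After Surgery (ERAS) guidelines between cardiac anesthesiologists, cardiac intensivists and cardiothoracic surgeons = 50" per cent, "Confidence limit =5" per cent, and a population of 1000 physicians across the two institutions. The result is given as: "This gave a minimum sample size two hundred and seventy eight physicians had selected to be included in the study".

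Under Study Procedures, 1. Randomization, the questionnaire "will be sent online", and "The random sample will be taken by use of random list". Under Ethical Considerations, "Informed consent will be obtained from study participants" or their representatives.

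The only outcome defined is the primary one: "Assesment of the knowledge of doctors to ERAS guidelines in cardiac surgery by using the grading system". The analysis section plans counts, percentages, means and standard deviations, with a general 0.05 significance level.

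The document gives no expected response rate, number of invitations, reminders, replacement of non-responders or reporting of response.

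**The concern.** An online questionnaire sent to a drawn sample will rarely be returned by everyone. The formula behind 278 has no response term and leaves no slack, so the 5-point limit is met only if 278 usable forms come back.

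The closing sentence can be read two ways. The words for a minimum and for inclusion point to completed forms. The word for selection could point to the number drawn and sent the form. On the second reading, every unanswered invitation widens the interval around the study's only defined outcome.

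A second issue applies on either reading. If those who answer know more, or less, than those who do not, the estimated proportion is shifted and the confidence interval does not show it. A reader would need the number invited and the response rate to weigh that.

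**Working it through.** **Inputs from the Sample size section:** N = 1000, p = 0.50, d = 0.05, z = 1.96 (95% confidence).

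**Step 1. Reproduce 278.** The precision formula for one proportion with finite population correction is

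n = N·p(1−p) / [(d²/z²)(N−1) + p(1−p)]

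= 1000 × 0.25 / [(0.0025/3.8416) × 999 + 0.25] = 250 / 0.90012 = 277.74, rounded up to **278**.

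**Step 2. Precision if 278 forms are completed.**

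Half-width = z·√[p(1−p)/n]·√[(N−n)/(N−1)]

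= 1.96 × √(0.25/278) × √(722/999) = **4.997 points**. At 277 it is 5.009. So 278 is exactly the number of completed forms that meets the limit. This treats the forms as a simple random sample of the 1000.

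**Step 3. Precision if only 278 are invited.** The documents give no response rate, so each rate below is an assumption. Forms returned = 278 × response, and p = 50% as planned. The last column gives the invitations needed for 278 returns, 278 / response.

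| Assumed response | Forms returned from 278 | Half-width (points) | Invitations for 278 returns |
|---|---|---|---|
| 90% | 250 | 5.4 | 309 |
| 80% | 222 | 5.8 | 348 |
| 70% | 195 | 6.3 | 398 |
| 60% | 167 | 6.9 | 464 |
| 50% | 139 | 7.7 | 556 |
| 30% | 83 | 10.3 | 927 |

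Below 278/1000 = 27.8% response, 278 forms could not be reached even by inviting all 1000.

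**Step 4. How demanding is the planning value?** At 50% the formula asks for the most forms. For illustration only, the same formula gives 254.7, so 255 forms (255/278 = 92%), at p = one third, and 197.5, so 198 forms (198/278 = 71%), at p = 20%. The plan's hypothesis is that the guidelines are not well known. If the share who know them is well below one half, some non-response is absorbed.

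**Step 5. Non-response bias.** Bias = (1 − response) × (difference between responders and non-responders). The difference that would produce a bias of 5 points is 5/(1 − response):

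- 80% response: 5/0.2 = 25 points
- 60% response: 5/0.4 = 12.5 points
- 50% response: 5/0.5 = 10 points

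These are break-even values. The documents support no estimate of the actual difference or its sign.

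**Step 6. Which reading fits the sentence?** A minimum sample size of physicians to be included is ordinarily a floor on those analysed. A doctor who never opens the form is not included in any usual sense, and consent is taken from participants, although that line is weak evidence either way. The contrary reading depends on one verb in a sentence that does not parse. Step 2 therefore applies, and Step 3 shows only what would follow if the weaker reading were intended.

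**The case for a change.** The strongest case for acting is that both readings leave something unwritten. If 278 are invited, the plan's own precision is missed at its own planning value. If 278 are completed, the team has no stated number to invite, and sending forms until 278 come back without counting invitations would hide how selected the respondents are. The study is one descriptive estimate, random selection supports it only as far as those selected reply, and a few sentences would close the gap.

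Part of this stands. The document is silent on response, 278 has no margin, and the number invited and the response rate belong in the report. But both can be settled in fieldwork and write-up, provided invitations are logged, without altering the design or the target. The precision loss depends on the weaker reading and on assumed rates, and at 80% response it is 0.8 points (5.8 against 5.0) in a survey where no decision rule or cut-off is tied to the 5-point limit.

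The bias argument is fair as a general caution. However, a larger draw would not cure it, and a comparison of respondents with the sampling list depends on what that list records, which the documents do not say.

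**Conclusion.** The concern does not call for a change. The figure of 278 is correct, and as a minimum number of doctors included it gives ±5.0 points at 50% and less elsewhere. The absent invitation number and response-rate report are gaps that a survey team would ordinarily fill: send enough forms to obtain 278, count those sent, and give the interval from the number returned.

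The size of the issue is conditional. It is nil for precision on the natural reading. On the other reading the half-width at 50% would be 5.4, 5.8 or 7.7 points at assumed responses of 90%, 80% or 50%. Non-response bias is neither shown nor excluded.

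The ±5.0 figure assumes a simple random sample of all 1000. The Randomization paragraph names anesthesiologists and intensive care physicians as recipients, whereas the population of 1000 also counts surgeons. That mismatch is a separate matter from non-response, but any further invitations would need to come from a list that covers all three groups.

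### The 278 rests on a 95% interval of ±5 points that the analysis section does not plan, and the sampling sentence leaves out the surgeons counted in N=1000

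*Combined protocol and SAP*

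**What the plan says.** All references are to the combined protocol and SAP.

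- **Statistical Analysis, I. Sample size.** At a 95% confidence level, the inputs are "Expected frequency of knowledge about Enhance Recovery After Surgery (ERAS) guidelines between cardiac anesthesiologists, cardiac intensivists and cardiothoracic surgeons = 50" percent, "Confidence limit =5" percent, and "Population size = 1000 (cardiac anesthesiologists, cardiac intensivists and cardiothoracic surgeons in Cairo University hospitals" and the National Heart Institute. The result: "This gave a minimum sample size two hundred and seventy eight physicians had selected to be included in the study". No power, null value or alternative is given.
- **VI. Study outcomes, primary outcome.** "Assesment of the knowledge of doctors to ERAS guidelines in cardiac surgery by using the grading system". The grading system has three levels: "Grade A (knows well (: more than 60 % correct answer", then Grade B (fair, 35 to 60%) and Grade C (knows nothing, below 35%).
- **Statistical Analysis, II, A. Descriptive statistics.** "1- Count and percentage", and mean and standard deviation for quantitative variables.
- **Statistical Analysis, II, B. Analytical statistics.** The whole entry is "The data will be analyzed and when $p<0.05$ will be considered statistically significant".
- **Hypothesis.** ERAS guidelines are not well known among doctors; no proportion is attached.
- **V. Study Procedures, 1. Randomization.** The questionnaire goes online to a random sample, drawn from a random list, of anesthesiologists and intensive care physicians. Surgeons are not mentioned there. They are named in the aim, the study design, the study population and the inclusion criteria.

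**The concern.** A sample size set by the width of a confidence interval makes sense only if that interval is reported. Here the listed measures stop at the percentage, so the one quantity that determined 278 has no place in the analysis. Three gaps follow.

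- The sample size speaks of knowledge as a yes/no characteristic with an expected frequency of 50%, while the primary outcome has three levels. No text says which level or levels the 50% describes.
- If an analyst adds an interval later, the ordinary formula misses the planned precision, because 278 already uses up the finite-population correction.
- The significance rule is the only inferential statement, and it names no test, comparison or null. It cannot be applied to a one-group statement that guidelines are not well known.

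The sampling sentence raises a related problem. Followed literally, it sends the questionnaire to two of the three target groups. The pooled estimate would then not describe the stated population, and N=1000 would be the wrong population size for the correction.

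**Working it through.** **Inputs** (Statistical Analysis, I. Sample size): z = 1.96 for 95% confidence, p = 0.50, d = 0.05, N = 1000.

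**1. Reproduce the plan's figure.**

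- Without a finite population: n0 = z² p(1−p)/d² = 3.8416 × 0.25/0.0025 = 384.16.
- With N = 1000: n = n0/[1 + (n0 − 1)/N] = 384.16/1.38316 = 277.74, rounded up to 278.

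The figure is right, and it depends on the finite-population correction.

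**2. Precision that 278 delivers.** The uncorrected half-width is 1.96 × √[p(1−p)/278]. The correction factor is √[(1000 − 278)/(1000 − 1)] = √(722/999) = 0.850.

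| True proportion | Uncorrected | Corrected |
|---|---|---|
| 50% | 5.88 points | 5.00 points |
| 30% | 5.39 | 4.58 |
| 20% | 4.70 | 4.00 |
| 10% | 3.53 | 3.00 |

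The half-width is largest at 50%, so 278 meets ±5 points whether the intended proportion is Grade A or Grades A and B together, provided the interval is corrected.

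**3. Fewer replies.** The documents give no expected response rate, so these counts are assumptions. Corrected half-width at 50% = 1.96 × √(0.25/n) × √[(1000 − n)/999]:

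- 250 replies: 6.20 × √(750/999) = 5.4 points
- 222 replies: 6.58 × √(778/999) = 5.8 points
- 139 replies: 8.31 × √(861/999) = 7.7 points

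**4. Analysis section against the sample-size inputs.**

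| Needed to use the 278 | In the analysis section |
|---|---|
| A named proportion | Not given; the outcome is a three-level grade |
| A 95% interval | Not listed |
| The finite-population correction | Not listed |
| A null or named comparison for p<0.05 | Not given |

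**5. Population.** The aim, design, study population, inclusion criteria and the 1000 all cover three specialties; the sampling sentence covers two. A list without surgeons would have a different N. The documents do not split the 1000 by specialty, so the corrected width for such a list cannot be computed from them.

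**The case against.** The strongest reply is that this is a descriptive survey with little left to resolve. Much of that stands.

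- If counts and percentages are reported for all three grades, a reader can see A and A+B directly and can compute an interval. It would be too strong to infer that the primary result cannot be interpreted. What the reader does not get is the intended proportion or the interval on which the size was based.
- Grade A is labelled as knowing well, which matches the wording of the hypothesis, so Grade A is the natural reading. The ambiguity is confined mainly to the sample-size line, which says only knowledge. Since 50% is the worst case for precision, it does not alter the 278.
- A reader might treat 50% as the threshold for the hypothesis and judge the results as above or below it. The documents do not support this: 50% is a planning input.
- A reader might infer that the sample is too small because the uncorrected formula asks for more. The sample-size section defines its population as the three specialties at the named institutions and claims nothing wider.
- A descriptive study needs no test. A missing benchmark is a defect only if a formal verdict is intended, and an estimate with its interval is sufficient.
- The significance rule may be meant for comparisons between specialties. That is possible, but none is named.
- The omission of surgeons may be a drafting slip, since every other section includes them. One cannot conclude that they will be left out, only that the text as written says so.

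**Conclusion.** The point holds in a limited form. The 278 is correct for estimating one pooled proportion to ±5 points at 95% confidence in a population of 1000. The analysis section does not plan that interval, does not tie the 50% to a grade, and gives a significance rule with nothing to apply it to.

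The size is modest: at 278 replies and 50%, ±5.0 points if the correction is planned and ±5.9 if an ordinary interval is used. This assumes a simple random sample from a list of 1000, with 278 replies received.

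The sampling sentence is a direct inconsistency with the rest of the document. Read literally, it omits one of three target groups and undermines both the pooled estimate and the N used in the correction. Both matters should be settled before the data are seen; neither shows that the sample size is wrong.

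**What to change.** 1. **Primary estimate.** Add to the analysis section: *The primary estimate is the proportion of physicians in Grade A (sponsor to confirm), pooled over the three specialties and shown with the full A/B/C distribution, with a 95% CI using the finite-population correction, where n is the number of replies and N the size of the sampled list. The expected 50% in the sample size refers to this proportion.*
2. **Sampling sentence.** Either amend it so that the random list covers all three specialties, or restrict the stated population and restate N, with the sample size recalculated for that N.
3. **Significance rule.** Report the primary outcome as an estimate with its CI. Keep p<0.05 only for comparisons that are named, for example between specialties if these are intended; otherwise delete it. A benchmark for *not well known* is optional. If one is used, it must be a share of doctors, distinct from the 60% correct-answer cut-off that grades a single doctor, and be fixed before the data are seen.

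**Cost.** A few lines of text and the sponsor's decisions on the proportion, the sampled population and the use of p<0.05. If all three specialties stay in, the 278 stands and no extra participants are needed, though the list must include surgeons. The downside is that the reported interval will be visibly wider than ±5 points near 50% if fewer than 278 reply.
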